2.3.3 ASSESSMENT OF POTENTIAL RISKS

- Drawing of blood can be associated with pain, bruising, anemia, and possible infection.
- A genetic diagnosis could be missed, with clinicians thinking it is unlikely to be present since the genetic testing is negative.
- If parents/guardians and/or biological parents opt-in to receive secondary findings for their child and/or themselves, this information may improve their overall health, but also may provoke anxiety in learning about the information.
- If parents/guardians and/or biological parents opt-out of receiving secondary findings, they will not receive information that could potentially impact their health or their child's health.
- Despite the presence of a COC, PHI related to a genetic diagnosis may need to be revealed to government agencies or other organizations involved in the research.
- For a critically ill infant, a preliminary diagnosis may be disclosed to the clinical team without time for confirmatory testing. Potential therapy may be initiated that may not be necessary.
- If a diagnosis is made, the information may not be provided to the clinical team in sufficient time to improve outcome.
- It is not clear how reporting of variants of unknown significance will impact care and outcome.

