4 STUDY DESIGN

4.1 OVERALL DESIGN

This multicenter, prospective, clinical trial will estimate the diagnostic yield of NewbornDx and rWGS testing and assess the clinical utility of genomic sequencing among high-risk infants with signs/symptoms consistent with a possible genetic disorder. The relative cost effectiveness of each testing method will be evaluated through simulation.

There are three components to this study:

1. Infants will undergo SOC diagnostic testing as well as NewbornDx and rWGS in parallel. Genetic sequences via NewbornDx and rWGS will be generated for the infant (proband) and when available, the biological parents, and analyzed together. NewbornDx and rWGS test results will be returned to the infant's clinician, medical record and parent/guardian. Those infants analyzed as a duo or trio will have a retrospective analysis done of only the infant's data to determine if the same result would have been obtained with and without parent samples. Clinical utility will be measured by clinician opinion and changes in the infant's care as a result of the genetic sequencing test results. QoL and medical resource utilization will be collected by parent survey monthly, until the infant is one year CGA.
2. A retrospective chart review of neonates with suspected genetic disorders completed at 3 sites, will be used to elucidate 1-year cost and health outcomes that would have been incurred in the absence of available NewbornDx and rWGS testing. The retrospective review will include 300 neonates born 12-18 months prior to the start of the study and performed under a separately submitted amendment to the central IRB. The cost and health outcome data will be used in an economic evaluation comparing NewbornDx, rWGS, and SOC over 1-year and a child's lifetime time trajectory.
3. A user-friendly clinical reference database will be developed to provide medical providers and families with information about genetic disorders, treatments, clinical trials and advocacy groups. A qualitative assessment of the clinical reference database will be conducted through surveys of clinicians involved in the infants' care. Once the database is completed and prior to implementation of the clinical reference database into this study, an amendment will be submitted to the IRB along with the survey.

Hypothesis #1: NewbornDx will detect at least 60% of the diagnoses identified by rWGS

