Secondary/incidental findings for an infant will not be actively sought. A dedicated analysis of the ACMG 59 secondary gene list will not be done. If a secondary/incidental finding is found during the infant analysis, the laboratory will only report it if both criteria 1 and 2 are met and either 3a or 3b:

1. The parent/guardian opted to receive secondary findings for the infant, AND
2. The disorder onset may occur in childhood, AND
3. At least one of the following:
 - a) The disorder is medically actionable AND/OR
 - b) The disorder involves a gene on the "American College of Medical Genetics and Genomics (ACMG) list" of genes recommended for reporting of secondary findings at the time of testing

Secondary findings of conditions with an onset only in adulthood will not be returned for the infant. Only pathogenic or likely pathogenic variants are reported as a secondary/incidental finding if they have the potential to impact the infant during childhood.

The "ACMG list" refers to the current list of genes recommended to report as secondary findings. WGS covers all 59 genes currently recommended by the ACMG to return as

secondary findings, NewbornDx covers 30 of those genes. There are 52 genes on the ACMG list that may occur in childhood. In order to account for how the ACMG list might evolve during the study period, the ACMG list at the time testing is done will be used. Therefore, the list used for the first infant enrolled may be different than the list used for the last infant enrolled. If the ACMG list evolves during the study period, we will not retrospectively change what was initially reported; this aligns with current clinical practice.

Primary and secondary findings for the infant, if reportable, will be included in one report from each laboratory.

Secondary Findings for a Biological Parent

A secondary finding for a biological parent may be identified through WGS when conducting the infant's phenotypically driven analysis. Secondary findings for a parent will not be actively sought and a dedicated analysis of the ACMG 59 secondary gene list will not be done. There may be cases in which a biological parent elects to receive secondary findings and the parent's sample does not undergo WGS. This could occur if the infant's samples have been processed prior to the receipt of the parent samples. Secondary findings for a biological parent will not be reported by Athena Diagnostics.

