8.4 ADVERSE EVENTS AND SERIOUS ADVERSE EVENTS

8.4.1 DEFINITION OF ADVERSE EVENTS (AE)

An Adverse Event for this study will only include the following:

- An untoward medical occurrence related to obtaining the study blood samples
- If findings for the infant thought to be secondary at the time results are reported are given to the research team, clinician or parent/guardian when the parent/guardian did not opt-in to receive secondary findings for their infant
- If secondary findings for a parent are reported to the research team, clinician or parent when the parent did not opt-in to receive parental secondary findings
- Intervention based on inaccurate result returned (testing error; provisional result not confirmed)
- Intervention based on wrong result returned (human error, result not accurately matched up with the correct infant)
- Untoward event related to an intervention initiated due to the genomic testing results (intervention that would not have been initiated without the genomic testing results)
- Loss of confidentiality related to study participation

- Any new untoward medical occurrence related to study participation or the genetic sequencing results
- A pre-existing condition that worsens in terms of frequency or intensity and the worsening is due to study participation/genetic sequencing results
- The infant dies due to error because the infant was enrolled in this study (erroneous result or misidentification)

Events not reported as Adverse Events for this study:

- A pre-existing condition at the time of enrollment
- A pre-existing condition that worsens in terms of frequency or intensity but the worsening is not related to study participation/genetic sequencing
- A new untoward medical occurrence that is not related to study participation/genetic sequencing results and does not result in death
- Death due to natural causes before genetic testing results are returned (i.e. prematurity)
- Death due to parent/guardian wishes to withdraw life sustaining treatment if an infant is determined to have a lethal condition by genetic testing

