Because a “gold standard” does not currently exist, it will not be possible to calculate the negative predictive value (NPV), sensitivity, or specificity of NewbornDx or rWGS. We will calculate the proportion for which there was clinical utility from genomic testing (change in drug treatment, surgical treatment, imaging, subspecialty consult, diet, other treatment, and redirection of care and/or withdrawal of life sustaining treatment). We will also calculate the proportion of testing where trios were ultimately required to confirm a diagnosis for rWGS and if this approach increased the number with a confirmed diagnosis. Kaplan-Meier (K-M) curves will be used to estimate the time from enrollment to molecular diagnosis (separately for NewbornDx and rWGS) including all enrolled infants and excluding infants without a diagnosis of a genetic disorder and those diagnosed by SOC before genomic results are returned. The analysis will count as positive only those diagnoses that are eventually confirmed. We will also use K-M to estimate age at diagnosis and survival. A model will be developed to predict, using information available at the start of symptoms, whether the NewbornDx ultimately yields a confirmed and actionable diagnosis. Such a model could help to further target NewbornDx to the population that would benefit most from it, especially if the model discrimination is high (c-statistic greater than .90). The model will be validated using bootstrap validation.

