Clinical utility of genomic sequencing	If clinical action was taken due to return of results Time from result to action taken Types of clinical actions taken (i.e. surgery, medication) Clinician opinion of utility	Binary: Yes/No Interval Categorical Ordinal	Modified Intention-to-Treat Analysis Dataset
If trio testing was required to obtain a diagnosis for rWGS	If Trios were done If Trios increased diagnostic yield	Binary: Yes/No; single endpoint Binary: Yes/No; single endpoint	Modified Intention-to-Treat Analysis Dataset
If enrollees did not receive a diagnosis	No confirmed diagnosis of a genetic disorder identified by any of the genomic sequencing tests	Binary: Yes/No; single endpoint	Modified Intention-to-Treat Analysis Dataset

*The infants who met the criteria for urgent testing may be analyzed separately.

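### The binary clinical-utility endpoint does not require the prompting result to be confirmed or correctly matched, so an intervention that section 8.4.1 calls an adverse event also counts as utility

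*Combined protocol and SAP*

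**What the plan says.** Section 4.1 sets the approach: "Clinical utility will be measured by clinician opinion and changes in the" infant's care that follow from the sequencing results. Section 9.4.2 lists clinical utility as a primary endpoint with four components: a binary one, the time from result to action, the type of action, and the clinician's opinion. The binary component reads "If clinical action was taken due to return of results" and is analysed in the modified intention-to-treat set.

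Section 9.4.1 turns it into a reported figure: "We will calculate the proportion for which there was clinical utility from genomic testing (change in drug treatment, surgical treatment, imaging, subspecialty consult, diet", with the list going on to other treatment and to redirection of care or withdrawal of life support.

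Section 8.4.1 defines adverse events for this trial. Two of its items are "Intervention based on inaccurate result returned (testing error; provisional result not confirmed") and "Intervention based on wrong result returned (human error, result not accurately matched up with the correct infant").

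The results table in section 8.2 allows a provisional result to guide an intervention before confirmation, and says what to record if the positive finding cannot then be confirmed. Section 2.3.3 names the risk in critically ill infants: "Potential therapy may be initiated that may not be necessary".

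**The concern.** The binary rule asks whether a result led to an action. It does not ask whether the result held up. An infant treated on a provisional finding that confirmation testing fails to support meets the rule, and so does an infant treated on a result belonging to another infant. Both are also adverse events by the protocol's own definition.

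The other result-based primary endpoints are handled differently. In section 9.4.2 the two yield endpoints require agreement between the platform and the confirmatory test, and the time-to-positive endpoints are limited to infants with a confirmed positive result. The synopsis describes utility partly as time to starting appropriate treatment; section 9.4.2 reduces this to time from result to action, without that qualifier.

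At stake is the meaning of a primary proportion. Section 3 justifies the endpoint as an assessment of impact on care, and section 9.4.1 labels the resulting proportion as clinical utility. A reader will not expect that figure to include interventions the trial also reports as adverse events.

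**Working it through.** **Step 1. How each kind of prompting result is scored.** The first column is the result that led to the action. The others apply sections 9.4.1 and 9.4.2, and the two items quoted from section 8.4.1.

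| Prompting result | Binary utility | Adverse event under those items |
|---|---|---|
| Confirmed positive | Yes | No |
| Provisional positive, later confirmed | Yes | No |
| Provisional positive, not confirmed | Yes | Yes |
| Result in error (testing error) | Yes | Yes |
| Result matched to the wrong infant | Yes | Yes |
| Negative result or reported VUS | Yes, if it led to an action | No |

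Rows three to five are the conflict.

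**Step 2. Whether anything removes rows three to five from the numerator.**

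- Section 9.3: the modified intention-to-treat set requires only that both sequencing results were returned. These infants stay in.
- Section 3, adjudication item 2: this covers disagreement between the clinician survey and the chart abstraction. An action correctly recorded in both, but based on a wrong result, raises no disagreement.
- Section 9.4.1: "The analysis will count as positive only those diagnoses that are eventually confirmed". This sentence stands in the Kaplan-Meier text on time to diagnosis. It restricts diagnoses, not clinical actions.
- Section 9.4.2: clinician opinion is a separate ordinal component. No rule lets it override a binary Yes.

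None does.

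**Step 3. The plan's own precision figure.** Section 9.2 gives 95% limits for a proportion with N = 400. The formula p ± z·√(p(1−p)/400) with z = 1.96 reproduces five of the six rows to two decimals. At p = 0.30 it gives 0.30 ± 1.96 × 0.0229 = 0.255 to 0.345, where the table has 0.25 to 0.35. With z = 2 that row becomes 0.254 to 0.346 and all six rows match. Nothing here depends on that difference.

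**Step 4. Size per infant.** Each affected infant contributes 1/400 = 0.25 percentage points. The documents give no rate for such actions and no expected utility proportion, so the counts below are assumptions. The 30% starting level is only one of the table's illustrative values. As written, 120/400 = 30.0% (95% CI 25.5 to 34.5).

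| Infants removed | Shift (points) | Proportion (95% CI) |
|---|---|---|
| 4 | 1.0 | 116/400 = 29.0% (24.6 to 33.4) |
| 8 | 2.0 | 112/400 = 28.0% (23.6 to 32.4) |
| 20 | 5.0 | 100/400 = 25.0% (20.8 to 29.2) |

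The half-width at 30% is about 4.5 points. Under these assumptions the shift stays inside sampling error unless such actions are common.

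**The case against.** **The wording is an attribution rule.** The plan says the action must be due to the result, which is narrower than any action that follows one. That is correct, and a reader who infers that coincidental later changes count has misread it. But an intervention started on a wrong result is due to that result, so the conflict remains.

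**The harm is visible elsewhere.** These events are reported as adverse events, section 9.4.1 reports the proportion of positives confirmed, and clinician opinion can register low utility. All of this stands: nothing is hidden. It does not change what the binary proportion counts.

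**Exposure is narrow.** Section 6.1.1 requires confirmation before positive results are returned, except provisional ones. It limits provisional release to cases where a treatment exists and delay could cause irreversible harm, and bars it for lethal conditions. At Mount Sinai, provisional findings made only by rWGS are withheld from the clinical team. This stands and argues for a small number.

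**Test errors also lower the figure.** A reader might infer that errors can only inflate utility. The documents do not support that. Sections 2.3.1 and 2.3.3 expect some missed diagnoses, and a missed diagnosis removes actions that would have followed. Only the specific actions at issue here are confined to adding to the numerator; the net direction of all errors is unknown.

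**Incidental findings.** Section 6.1.1 says "Primary and secondary findings for the infant, if reportable, will be included in one report from each laboratory", so a reader might infer that actions prompted by an opted-in incidental finding also contaminate the endpoint and add several points. The objective concerns the utility of genomic sequencing, and acting on such a finding can reasonably count. These findings are not actively sought, and no rate is given. Excluding them would be a preference, not the correction of an error.

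**Conclusion.** The point holds on the definition. Sections 9.4.1 and 9.4.2 count as utility a set of interventions that section 8.4.1 defines as adverse events, and no other rule removes them. It is limited to actions whose only basis was a positive result not confirmed, or a result found to be erroneous or misassigned. Actions on provisional results later confirmed are not in question.

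The size is 0.25 percentage points per infant, taking the modified intention-to-treat denominator as 400. The total cannot be estimated from the documents and is probably small. A claim of material inflation would rest on assumed rates. The analysis is descriptive (section 9.1), so no test result is at risk; what suffers is the interpretation of a primary proportion. It should be settled before analysis because the repair is cheap.

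One limit: the Clinical Actions form and the clinician survey are not reproduced in the documents, so the form may already record which result prompted each action.

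**What to change.** In sections 9.4.1 and 9.4.2:

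- Link each action on the Clinical Actions form to the result that prompted it, if the form does not already do so. The Schedule of Activities shows that the laboratories already send whether a preliminary result was returned provisionally and whether confirmation testing confirmed it, so those fields can be merged.
- Do not score as utility Yes an action whose only basis was a positive result that was not confirmed, or a result found to be erroneous or misassigned. The yield endpoints in section 9.4.2 already supply a definition of confirmed.
- Report those actions as a separate proportion, cross-tabulated with the corresponding adverse events, and give the utility proportion with and without them.
- Keep actions on negative results and reported VUS countable with no test of correctness. Section 9.4.1 states that there is no gold standard, so such a test could not be applied.
- Optionally show actions prompted only by an incidental finding as a separate line; they need not be excluded.

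The cost is at most one link on an existing electronic form plus analysis wording. The utility proportion may come out slightly less favourable. Clinical care does not change.

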Misinterpretation of results: We expect to miss a small number of structural variants (SVs) using short read rWGS (NewbornDx does not detect structural variants) that are causal. We will monitor the percentage of identified SVs and be careful not to label cases with a negative result as not genetic in origin. Experienced personnel will perform the genomic testing according to well-established protocols. Although we may not find a result, this does not mean the infant will not continue to have symptoms or even have a genetic disorder. Similarly, the infant’s health may not improve during this study; it may get worse or stay the same. All infants will continue to receive routine care as directed by the clinical team, including routine NBS and other genetic testing.

Risk of discrimination associated with genetic testing: Federal and State laws generally make it illegal for health insurance companies, group health plans, and most employers to discriminate against a person based on their genetic information. The Genetic Information Non-discrimination Act (GINA) indicates that genetic information cannot be used by certain health insurance companies when making decisions about eligibility for health insurance or how much insurance costs. These insurance companies can still use any genetic information to help them decide whether or not they will pay health insurance claims. This law also indicates that employers with fifteen or more employees may not use genetic information when making decisions to hire, promote, or fire an individual or when setting the terms of employment. Protections by this law may not apply to certain military, veterans and federal employees. These laws do not protect against genetic discrimination by companies that sell life, disability, or long-term care

insurance. Information regarding the protections and limitations of Genetic Information Nondiscrimination Act (GINA) will be included in the ICF.

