3 OBJECTIVES AND ENDPOINTS

Primary Objectives	Endpoints		Endpoint Justification
To estimate the diagnostic yield of NewbornDx and rWGS in identifying genetic disorders of unknown etiology	Primary	A confirmed genetic disorder detected by NewbornDx A confirmed genetic disorder detected by rWGS	Assess diagnostic capability of the platforms
	Secondary	For diagnoses by rWGS, if trio testing was required to confirm a diagnosis	Assess need for including biological parents
To assess the clinical utility of genomic sequencing	Primary	Time from sample collection to positive test result	Assess the timeliness of an accurate result
	Primary	Clinical utility of genomic sequencing	Assess impact on care
	Secondary	If the infant does not receive a diagnosis, calculated at discharge and at 1year CGA	Assess the clinical impact of platform(s)
Secondary Objectives	Endpoints		Endpoint Justification
To examine the economic impact and health outcomes of NewbornDx and rWGS in infants compared with SOC diagnostic testing, over a one-year and lifetime horizon	Secondary	One-year cost-effectiveness of NewbornDx and rWGS compared with SOC testing	Assess economic value of alternative testing strategies
	Secondary	Lifetime cost-effectiveness of NewbornDx and rWGS, compared with SOC testing	Assess economic value of alternative testing strategies
To develop and qualitatively assess the web-based clinical reference database of supporting information for medical providers and parents	Secondary	Satisfaction of the web-based clinical reference database	Assess ease of use and usefulness of information among medical providers
Exploratory Objectives	Endpoints		Endpoint Justification
To inform the NewbornDx panel with findings from rWGS that were not identified with NewbornDx	Exploratory	Conditions detected by rWGS that were not detected by NewbornDx	Expand and improve the diagnostic accuracy of the NewbornDx panel

How endpoint(s) will be adjudicated

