7.2 PARTICIPANT DISCONTINUATION/WITHDRAWAL FROM THE STUDY

An infant's parent/guardian or a biological parent can withdraw their own participation at any time and is not obligated to state the reason for withdrawal. However, the investigator should make a reasonable effort to ascertain the reason for withdrawal while fully respecting the parent/guardian's or biological parents' rights.

An investigator may discontinue or withdraw an infant from the study for the following reasons:

- A clinical diagnosis was determined prior to completing the genomic testing for the infant
- Withdrawal is requested by the NIH or DSMB
- If the infant meets an exclusion criterion (either newly developed or not previously recognized) that precludes further study participation (i.e. CMV testing that came back positive after enrollment)
- If the blood samples cannot be safely obtained from the infant
- The parent/guardian withdraws consent for the infant

The reason for discontinuation of the infant or biological parent will be recorded in the study database. An infant for whom the parent/guardian provided consent but who does not receive the study intervention may be replaced. An infant for whom the parent/guardian provided consent and who received the study intervention and was subsequently withdrawn from the study will not be replaced.

In the event of an infant death prior to the completion of genetic testing, the testing will continue to be done unless the parent/guardian indicates otherwise. There is a potential to provide information regarding a hereditary disorder for future children.

If an infant is withdrawn from the study, the data already collected on the infant may be used unless the parent/guardian indicates otherwise in writing.

The following actions will be taken at the local study site and laboratories as applicable after receiving a request to withdraw:

- Upon receipt of request to withdraw, the enrolling site will notify RCIGM and Athena (Quest) of withdrawal of the infant and/or the biological parent(s). Mount Sinai will also notify Sema4.

- The enrolling site or laboratories that are in possession of unused blood from the infant and/or the biological parent(s) will ensure blood samples are destroyed.
- Isolated DNA will be destroyed. The laboratories will permanently break any link between personal identifying information and sequencing data files from the infant and/or the biological parent(s).

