9.3 POPULATIONS FOR ANALYSES

- ICF Dataset: All families who were approached for study participation
- Intention-to-Treat (ITT) Dataset: all consented infants
- Modified Intention-to-Treat Dataset: all consented infants for whom both NewbornDx and rWGS genomic sequencing results were returned
- Per-Protocol Dataset: all consented infants who received both NewbornDx and rWGS (modified intention-to-treat dataset) and completed the study period for the analysis of the primary and secondary objectives without clinically important protocol deviations. Clinically important protocol deviations will be identified and documented prior to the database lock.
- Time to Molecular Diagnosis Dataset: The Modified Intention-to-Treat Analysis Dataset excluding the infants who did not have a confirmed positive result
- Urgent Testing Dataset: All infants who required urgent testing per section 8.1

- Safety Analysis Dataset: All infants for whom blood specimens were obtained or data collected

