9.4 STATISTICAL ANALYSES

9.4.1 GENERAL APPROACH

All analyses will be descriptive. We will calculate the proportion and 95% CI among enrolled infants with confirmed genetic disorders detected by NewbornDx, by rWGS, by NewbornDx but not rWGS, and by rWGS but not NewbornDx. We will also calculate the 95% CI for the ratio of the proportion detected by NewbornDx relative to the proportion detected by rWGS⁶⁹. Although detection by SOC is an exclusion criterion, some infants will receive a diagnosis by SOC after enrollment. We will therefore also calculate the proportion and 95% CI of those receiving a diagnosis by SOC prior to the time that results from NewbornDx or rWGS become available. We will calculate the proportions and CIs for enrollees with no confirmed diagnosis of a genetic disorder. These will be calculated at discharge and at 1 year CGA. We will calculate the proportion of infants with conditions detected by NewbornDx that were not listed as part of the differential diagnosis at enrollment. The same calculation will be performed for rWGS. We will calculate the positive predictive value (PPV) of NewbornDx and rWGS (i.e. the proportion of positives that are confirmed by Sanger or PCR).

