9.4.2 ANALYSIS OF THE PRIMARY EFFICACY ENDPOINT(S)

Primary Endpoints	Definition	Scale and measure	Populations for which the analysis will be conducted
A confirmed positive result detected by NewbornDx	If NewbornDx and the confirmatory test have the same positive finding	Binary: Yes/No; single endpoint	Modified Intention-to-Treat Dataset
A confirmed positive result detected by rWGS	If rWGS and the confirmatory test have the same positive finding	Binary: Yes/No; single endpoint	Modified Intention-to-Treat Dataset
Time to a positive result by NewbornDx *	Among those who have a confirmed positive result at one year CGA by NewbornDx, rWGS, or another genetic test, comparison of date/time of sample collection to date/time of completion of NewbornDx prior to confirmation testing	Interval: Hours; single endpoint	Time to Molecular Diagnosis Dataset
Time to a positive result by rWGS*	Among those who have a confirmed positive result at one year CGA by NewbornDx, rWGS, or another genetic test, comparison of date/time of sample collection to date/time of completion of rWGS prior to confirmation testing	Interval: Hours; single endpoint	Time to Molecular Diagnosis Dataset
Time to a result by NewbornDx*	Among all babies tested, comparison of date/time of sample collection to date/time of completion of NewbornDx prior to confirmation testing	Interval: Hours; single endpoint	Modified Intention-to-Treat Dataset
Time to a result by rWGS*	Among all babies tested, comparison of date/time of sample collection to date/time of completion of rWGS prior to confirmation testing	Interval: Hours; single endpoint	Modified Intention-to-Treat Dataset
Time from enrollment to a positive result	Among those who have a confirmed positive results at one year CGA by NewbornDx, rWGS or another genetic test,	Interval: Hours; single endpoint	Time to Molecular

Primary Endpoints	Definition	Scale and measure	Populations for which the analysis will be conducted
detected by NewbornDx*	comparison of date/time of informed consent to date/time of completion of NewbornDx prior to confirmation testing		Diagnosis Dataset
Time from enrollment to a positive result detected by rWGS*	Among those who have a confirmed positive results at one year CGA by NewbornDx, rWGS, or another genetic test, comparison of date/time of informed consent to date/time of completion of rWGS prior to confirmation testing	Interval: Hours; single endpoint	Time to Molecular Diagnosis Dataset

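### The table in 9.4.2 counts only sequencing diagnoses in the endpoint for infants who did not receive a diagnosis, so an infant diagnosed by another genetic test is reported as not diagnosed

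*Combined protocol and SAP*

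**What the plan says.** The endpoint appears in three places.

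- Section 3 lists it as a secondary endpoint under the clinical utility objective: "If the infant does not receive a diagnosis, calculated at discharge and at 1year CGA". No test is named. The justification given is the clinical impact of the platforms.
- Section 9.4.1 says "We will calculate the proportions and CIs for enrollees with no confirmed diagnosis of a genetic disorder", and then "These will be calculated at discharge and at 1 year CGA". No test is named here either. Just before this, 9.4.1 says that some infants will be diagnosed by standard of care (SOC) after enrollment, and it plans a proportion for SOC diagnoses made before the sequencing results are available.
- The table in 9.4.2 has a row for enrollees who did not receive a diagnosis. Its definition column reads "No confirmed diagnosis of a genetic disorder identified by any of the genomic sequencing tests". The row gives no time point and uses the modified intention-to-treat (mITT) set, which 9.3 defines as "all consented infants for whom both NewbornDx and rWGS genomic sequencing results were returned".

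Other rows of the same table use a wider notion of diagnosis. Those for time to a positive result start from infants described as "Among those who have a confirmed positive result at one year CGA by NewbornDx, rWGS, or another genetic test".

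**The concern.** The label of the 9.4.2 row is broader than its definition. A reader of the label will take the figure to be the share of infants who reach 1 year CGA with no genetic diagnosis. The definition delivers the share with no diagnosis from the study's own sequencing. The two differ by the infants whose diagnosis came only from another test.

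The protocol expects other testing to go on. Section 2.3.1 states: "All infants will continue to receive routine care as directed by the clinical team, including routine NBS and other genetic testing". The same section expects short-read rWGS to miss a few causal structural variants, and the table of variant types in 6.1.1 lists them as not detected by NewbornDx. Section 2.3.3 names a diagnosis missed after negative testing as a study risk. Sensitivity and negative predictive value cannot be estimated (9.4.1), so diagnoses recorded from other tests are the most direct evidence on that risk that the trial can offer. The narrow definition hides them inside the undiagnosed group.

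**Working it through.** **Step 1. Do the affected infants stay in the analysis set?** The mITT set needs both sequencing results. The withdrawal ground in 7.2 is "A clinical diagnosis was determined prior to completing the genomic testing for the infant", which covers only diagnoses made before sequencing is complete. An infant negative on both tests and diagnosed afterwards, for example by microarray, remains in mITT. The three sections then treat that infant as follows.

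| Source | Route of diagnosis | Time points | Status at 1 year CGA |
|---|---|---|---|
| Section 3 | not restricted | discharge, 1 year CGA | diagnosed, on the natural reading |
| 9.4.1 | not restricted | discharge, 1 year CGA | diagnosed, on the natural reading |
| 9.4.2 | study sequencing only | none given | not diagnosed |

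**Step 2. What can move the 9.4.2 figure between discharge and 1 year?** Only a sequencing result returned after discharge (8.2), a re-analysis after a change in phenotype (6.1.1), or the possible re-analysis of variants of unknown significance (VUS) at the end of the study (8.2). A later clinical diagnosis cannot.

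**Step 3. Size.** The one related figure in the plan is in 9.2: 40% to 60% of 400 infants are expected to have a genetic diagnosis. It reproduces: 400 × 0.40 = 160 and 400 × 0.60 = 240.

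Assumption A: these are sequencing diagnoses. Infants without a positive report then number 400 × (1 − 0.60) = 160 to 400 × (1 − 0.40) = 240. VUS cases are not positives under the protocol's definitions, so they stay in this base.

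Assumption B: a share s of these infants is diagnosed by another genetic test by 1 year CGA. The documents give no value, so s = 1%, 5% and 10% are shown. The count is n × s, rounded, and the gap between the two definitions is count / 400.

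| Without a positive report (n) | s = 1% | s = 5% | s = 10% |
|---|---|---|---|
| 160 | 2 (0.5 points) | 8 (2.0 points) | 16 (4.0 points) |
| 240 | 2 (0.5 points) | 12 (3.0 points) | 24 (6.0 points) |

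Worked example with n = 240 and s = 5%:

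- sequencing-only definition: 240/400 = 60.0% not diagnosed;
- any-test definition: (240 − 12)/400 = 228/400 = 57.0% not diagnosed;
- difference: 3.0 points;
- diagnosed by another test among those without a positive report: 12/240 = 5.0%, exact 95% CI 2.6% to 8.6%.

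For scale, the Wald 95% CI for 240/400 is 55.2% to 64.8%, a half-width of 4.8 points. The gap is not sampling error: it comes from applying two definitions to the same infants.

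The base of the assumed share matters. If 1% to 10% is applied to all 400 infants, the count is 4 to 40, or 1 to 10 points.

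**The case against.** The best defence is that 9.4.2 refines the other two statements and does not contradict them. Only the 9.4.2 table has a definition column. Section 3 and 9.4.1 leave the route of diagnosis open, and 9.4.1 does not say that any test counts. The objective concerns genomic sequencing and the justification concerns the platforms, so a sequencing-only figure would be a sensible output.

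Much of this stands. It would be too strong to say that the plan contains two explicit, opposed definitions. What remains is that the unrestricted sentence in 9.4.1 closely follows text about SOC diagnoses, that the same table elsewhere counts another genetic test, and that the row's label does not describe what the row measures.

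Three further inferences are tempting, and the documents do not support them.

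- *The analysis sets differ between 9.4.1 and 9.4.2.* 9.4.1 speaks of enrollees, which is not a dataset name in 9.3. But the 9.4.2 row uses the same word in its label and assigns mITT, so the set for this endpoint is stated.
- *The missing time point in 9.4.2 is a conflict.* It is a silence. Section 3 and 9.4.1 supply the time points, and two time points still mean something under a sequencing-only definition because results can arrive after discharge.
- *Diagnoses by other routes are not counted anywhere.* 9.4.1 plans the proportion diagnosed by SOC before sequencing results are available. What lacks a direct count is infants without a positive study test who are diagnosed by another test after the report.

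**Conclusion.** The point holds as a mismatch between a label and its definition. Following 9.4.2 as written, infants with a confirmed genetic diagnosis from another test are reported as not having received one, and the 1-year figure cannot respond to later clinical diagnoses.

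The size cannot be determined from the documents. Under assumptions A and B it is 2 to 24 infants, or 0.5 to 6.0 percentage points of 400.

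Severity is minor. Section 9.1 makes the whole analysis descriptive, Section 3 lists this endpoint as secondary, and neither primary yield estimate changes. A reader might infer that the count of other-test diagnoses would give a false-negative rate for sequencing. It would not: later testing follows clinical judgement, so the count is a lower bound on missed diagnoses and is not one minus the negative predictive value.

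**What to change.** 1. In 9.4.2, define the endpoint as no confirmed genetic diagnosis by NewbornDx, rWGS or another genetic test, at discharge and at 1 year CGA, in the mITT set already assigned to the row.
2. Report the sequencing-only figure as a separate row labelled *no diagnosis by study sequencing*, in the same set and at the same time points. The difference between the rows is then the number diagnosed only by another test.
3. Add a footnote that this number is a lower bound on missed diagnoses.

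The cost is one edited definition and one extra row. No new data are needed: the Clinical Genetic Tests form is completed as applicable through 1 year CGA (case report form schedule in Section 1), and parents are asked monthly about new tests and diagnoses (8.2). The downside is that later testing is not systematic, so the other-test count will be incomplete and a low or zero count could be misread as reassurance.
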